# Follow-up Visits Day 3, Day 5 and Day 8:

All subjects treated with IMP will attend the follow-up visits 2, 4 and 7 days after surgery (Day 3, 5 and 8):

The following procedures will be performed:

- Physical examination will be performed.
- **Vital signs** (including pulse [heart rate], blood pressure, respiratory rate, body temperature) will be recorded.
- Sample for **coagulation activation tests** (PT(INR), aPTT, TAT, F1+2, D-dimer, PS, PC, AT III, TT, TGT) will be taken.
- Samples for **clinical laboratory parameters** (hematology, clinical chemistry, urinalysis) will be taken:
  - **Hematology** (RBC, WBC, platelet count, hemoglobin, hematocrit)
  - Clinical chemistry (ASAT, ALAT, creatinine, creatinine clearance, BUN/Urea, γ-GT, AP, total bilirubin, potassium, sodium, calcium, chloride)
  - **Urinalysis** (pH, blood, WBC, protein, glucose, ketone bodies, nitrite, bilirubin, urobilinogen)
- Transfusion products (allogenic blood products) will be documented.
- **Concomitant medication or treatment** will be documented. The type of concomitant medication/treatment, dose/schedule, duration, and the indication the concomitant medication/treatment was given for will be documented.
- **AEs** will be documented.
- **Rebleeding episodes** will be recorded.

# Discharge from Hospital:

- The day of the discharge from hospital will be recorded at the **closing visit Day 36**.
- If the closing visit Day 36 (+35, up to Day 71 if required) is scheduled as a phone call, all tests and procedures requiring an in-person visit (physical examination, vital signs, samples for laboratory tests) must be performed on the day of hospital discharge:
  - Physical examination
  - **Vital signs** (including pulse [heart rate], blood pressure, respiratory rate, body temperature)
  - Sample for **coagulation activation tests** (PT(INR), aPTT, TAT, F1+2, Ddimer, PS, PC, AT III, TT, TGT)
  - o Samples for clinical laboratory parameters:
    - *Hematology* (*RBC*, *WBC*, *platelet count, hemoglobin, hematocrit*)
    - Clinical chemistry (ASAT, ALAT, creatinine, creatinine clearance, BUN/Urea, γ-GT, AP, total bilirubin, potassium, sodium, calcium, chloride)
    - Urinalysis (pH, blood, WBC, protein, glucose, ketone bodies, nitrite, bilirubin, urobilinogen)
  - Retention samples for viral safety laboratory parameters

• **Samples for virus serology laboratory parameters** (hepatitis B, hepatitis C, HIV)

# Closing Visit Day 36 (+35, up to Day 71 if required):

All subjects treated with IMP will attend a closing visit including the final safety examination, and a safety follow-up at least 5 weeks after the surgery, scheduled on Day 36 (+35, up to Day 71 if required).

Using a phone call instead of a protocol-directed in-person study visit is acceptable if all tests and procedures scheduled for Day 36 (+35) requiring an in-person visit (physical examination, vital signs, samples for laboratory tests), were performed on the day of hospital discharge. These results are to be entered in the eCRF in the fields provided for the closing visit.

The documentation of transfusion products, concomitant medication or treatment, and the recording of AEs can be performed by using a phone call. In addition, the follow-up of AEs can be completed with the subject by telephone (for the follow-up of AEs please refer to section 9.3.4).

An appropriate documentation of the phone call is kept.

The following procedures will be performed:

- A physical examination will be performed.
- **Vital signs** (including pulse [heart rate], blood pressure, respiratory rate, body temperature) will be recorded.
- Sample for **coagulation activation tests** (PT(INR), aPTT, TAT, F1+2, D-dimer, PS, PC, AT III, TT, TGT) will be taken.
- Samples for **clinical laboratory parameters** (hematology, clinical chemistry, urinalysis) will be taken:
  - **Hematology** (RBC, WBC, platelet count, hemoglobin, hematocrit)
  - Clinical chemistry (ASAT, ALAT, creatinine, creatinine clearance, BUN/Urea, γ-GT, AP, total bilirubin, potassium, sodium, calcium, chloride)
  - **Urinalysis** (pH, blood, WBC, protein, glucose, ketone bodies, nitrite, bilirubin, urobilinogen)
- Retention samples for viral safety laboratory parameters will be taken.
- Samples for virus serology laboratory parameters (hepatitis B, hepatitis C, HIV) will be taken.
- **Transfusion products** (allogenic blood products) will be documented.
- **Concomitant medication or treatment**: type of concomitant medication/treatment, dose/schedule, duration, and the indication the concomitant medication/treatment was given for will be documented continuously up to Day 36 (+35).
- **AEs** will be recorded continuously up to Day 36 (+35).

Further details on the visit schedule that will be used for the assessment of the efficacy and safety parameters in this study are presented in section III, Flowchart of Study.

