# III. FLOWCHART OF STUDY

Study Schedule Day	D-42 to D-1	D-2 to D1	D1	D1	D1	D1	D2	D3	D5	D8	D36 (+35)
Assessments Visit		Prior	Surgery			Follow-	Follow-	Follow-	Follow-		
	Screening	surgery (Baseline)	prior 1 st dose	pre- dose	post- dose	end of surgery	up	up	up	up	Closing
Informed consent	•										
Check/re-check of inclusion / exclusion criteria	•	• 									
Demographic data	•										
Classification of type of surgery	•										
Recording expected blood loss		•									
Body weight	•	•2									
Physical examination	•	•2					•	•	•	•	•3
Pregnancy test, only in females of childbearing potential	•	•2									
Medical and surgical history	•	•4									
Viral safety: Collection of retention sample	•										• 
Virus serology (hepatitis B, hepatitis C, HIV)	•										• 
Vital signs	•	•	•	•	•	•	•	•	•	•	• 
Hematology and clinical chemistry	•	•2	•			•	•	•	•	•	• 
Urinalysis	•	• 					•	•	•	•	• 
Markers of coagulation (coagulation activation tests)	•	•2	•		•5	•6	•	•	•	•	• 
Plasma concentration of fibrinogen activity (Clauss assay)	•	•2	•		•5	•6	•				
FIBTEM A10 (ROTEM)	•	•2	•	٠	•5	•6	•				
Maximum clot firmness (MCF) (ROTEM)	•	•2	•	•	•5	•6	•				

<sup>1 Diagnostic tests will be repeated at the investigator's discretion.

<sup>2 Diagnostic tests have to be done prior to surgery. In case of short time-period between screening and baseline (≤ 2 days) these tests have only to be repeated based on medical judgment of the investigator. If not repeated, screening results will serve as baseline.

<sup>3 Diagnostic tests are required as part of the closing visit. In case the closing visit is scheduled as a phone call, these tests can be performed on the day of hospital discharge.

<sup>4 Previous medication: change from screening.

<sup>5 Tests have to be done only 15 and 90 minutes after start of 1st IMP administration.

<sup>6 Tests (*Markers of coagulation, Clauss assay, FIBTEM A10, MCF, coagulation factors*) have to be done '90 min after start of 1st IMP administration' and at the 'end of surgery'. In case of a short time-period between these two time points (<30 min) these tests have only to be repeated based on medical judgment of the investigator.

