# 9.2.1.5 Retention Samples

In order to respond rapidly to any reports on additional viral infections, a pre-treatment serum sample (5 mL) from each subject included in the study must be taken pre-dose and stored at -70 °C for possible future testing (screening visit).

At closing visit (Day 36) an additional serum sample (5 mL) must be taken and stored up to 6 months after study end.

Viral safety retention samples will be analysed in the **central laboratory** (if applicable).

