4.0 Introduction

This SAP describes the statistical methods to be used during the reporting and analyses of data collected under Biotest AG Clinical Study Protocol 995.

This SAP should be read in conjunction with the Clinical Study Protocol (CSP) and eCRF. This version of the plan has been developed using the CSP version 4.0, dated 04DEC2019 and version 4.2 UK, dated 04AUG2020 and eCRF version 3.0, dated 15OCT2020. Any further changes to the CSP or eCRF may necessitate updates to the SAP.

The purpose is to finalize a SAP so that programming can start. Versions of the SAP up to initial sponsor approval will be known as a draft SAP. If any updates of the SAP are required, for example due to changes of the CSP or eCRF, then this version has to be approved and signed before locking any data for the interim or final analysis.

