12.6.3 Laboratory Data

The following clinical laboratory variables will be summarized for the overall population, and separately by type of surgery (spinal and abdominal surgery):

Hematology	Red blood cells (RBC), white blood cells (WBC), platelet count, hemoglobin, hematocrit, neutrophils (absolute and %), lymphocytes (absolute and %), eosinophils (absolute and %) and basophils (absolute and %)
Biochemistry	Aspartate aminotransferase, alanine aminotransferase, creatinine, creatinine clearance (Cockcroft and Gault), blood urea nitrogen (BUN), urea, gamma-glutamyltransferase (γ -GT), alkaline phosphatase (AP), total bilirubin, direct bilirubin, indirect bilirubin, potassium, sodium, calcium and chloride
Urinalysis	pH, blood, WBC, protein, glucose, ketone bodies, nitrite, bilirubin and urobilinogen
Markers of Coagulation	PT, INR, aPTT, TAT, F1+2, D-dimer, PS, PC, AT III, TT and ETP(TGT)
Coagulation factors	FII, FV, FVII, FVIII, FIX, FX, FXI, FXIII and vWF

Note: Protein C (PC) is also referred to as Factor XIV. Direct bilirubin and indirect bilirubin are only assessed in case of an elevated bilirubin value and are thus not generally included in statistical summaries.

Quantitative laboratory parameters reported as "< x" or "y" > will be imputed with x/2 and y, respectively, for inclusion in summary statistics. The reported value will be presented in listings.

Descriptive statistics for clinical laboratory values (in SI units) and changes from baseline at each scheduled assessment visit (as stated in Flowchart of study) with the exception of urinalysis parameters and direct/indirect bilirubin will be presented by treatment and treatment arm.

Laboratory results of all hematology, biochemistry, urinalysis parameters and PT/INR, aPTT will be categorized with respect to the laboratory specific reference ranges as normal/abnormal (i.e., high [H], low [L], where applicable). Abnormal values will be further classified with respect to clinical relevance by the investigator. The results and percentages will be summarized by visit and overall for each treatment and treatment arm.

Shifts from baseline to each post-baseline visit for all laboratory variables (except direct and indirect bilirubin) will be summarized by treatment and treatment arm using number and percentage of subjects.

In addition, a shift summary of hematology for number of subjects with change from normal or not clinical significant to clinical significant will be presented.

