12.6.6 Viral Status

A shift table from screening to closing visit for virus serology parameters (hepatitis B, hepatitis C and HIV) will be summarized by treatment and treatment arm using number and percentage of subjects.

Listings for viral status will be created respectively for the SAF.

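### The SAP has no sample-date rule for closing-visit data, so discharge-day tests allowed by CSP 4.3 UK, virus serology included, would be tabulated as the Day 36–71 result

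*Protocol*

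**What the plan says.** **Protocol (version 4.3 UK, 6 September 2021).** Section 7.1 sets the closing visit at Day 36, extendable by 35 days to Day 71, as a safety follow-up no earlier than five weeks after surgery. A phone call may replace it. In that case, under the Discharge from Hospital heading, all tests that need the subject present "must be performed on the day of hospital discharge". The list there covers physical examination, vital signs, coagulation activation tests, hematology, clinical chemistry, urinalysis, the retention sample and "Samples for virus serology laboratory parameters". Footnote 3 of the flowchart (section III) carries the same option: "In case the closing visit is scheduled as a phone call, these tests can be performed on the day of hospital discharge". On data entry, the Closing Visit text is explicit: "These results are to be entered in the eCRF in the fields provided for the closing visit". The amendment log dates the option to version 4.3.

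**SAP (19 June 2023).** Section 4.0 states its base: "This version of the plan has been developed using the CSP version 4.0, dated 04DEC2019 and version 4.2 UK". Section 8.10 lists the visit labels. It puts completers' closing data under Closing Visit and early discontinuers' closing data under Early Discontinuation. It has no discharge label, no visit window and no rule based on sampling date. Section 4.1, on changes from the protocol, does not mention the phone-call option. Section 12.6.6 plans "A shift table from screening to closing visit for virus serology parameters (hepatitis B, hepatitis C and HIV" and so on, by treatment and treatment arm. Sections 12.6.3 and 12.6.4 summarise laboratory values and vital signs by visit, with laboratory shifts to every post-baseline visit.

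**The concern.** Viral status is a named safety endpoint, and the screening-to-closing shift table is the only summary planned for the serology. A reader of that table would take the closing column as evidence from at least five weeks after exposure, because that is how the protocol defines the visit. If some entries come from the day of discharge, a count of subjects with no change covers a shorter interval for them, and nothing in the specified table shows it. The same label also feeds the closing rows for hematology, chemistry, urinalysis, coagulation markers and vital signs, where samples nearer to surgery could be combined with late ones.

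The columns may also differ in timing. Cryoprecipitate is the comparator only in the UK and FFP only in the spinal part. If the option exists only in the UK, the FFP and cryoprecipitate columns would have different sampling times, and the BT524 column would mix both.

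**Working it through.** **1. Reproduce the protocol's window.** Surgery is Day 1, so days since surgery = study day − 1.
- Upper limit: 36 + 35 = Day 71, as the protocol states.
- Day 36: 36 − 1 = 35 days = 5.0 weeks. Day 71: 71 − 1 = 70 days = 10.0 weeks. This agrees with the follow-up of at least five weeks.

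**2. Follow one subject through the rules.** Take a subject tested at discharge and closed out by phone within the window.
- Protocol 7.1: the discharge results go into the closing-visit fields of the eCRF.
- Protocol 7.2 accepts a phone call as the closing visit, so the subject counts as a completer under SAP 8.8.
- SAP 8.10: a completer's closing data are labelled Closing Visit.
- SAP 12.6.3, 12.6.4 and 12.6.6: that label is what is tabulated.

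No step refers to the sampling date. The mislabelling follows from the stated rules and does not depend on a detail left open.

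**3. Possible size of the gap.** The documents give no distribution of discharge days for PMP subjects. As an assumed range I use values within the length-of-stay categories of SAP 12.5.3.6. Stay is discharge date minus surgery date, so discharge day = stay + 1.

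| Stay (days) | Study day of sample | Days before Day 36 | Days before Day 71 |
|---|---|---|---|
| 7 | 8 | 28 | 63 |
| 14 | 15 | 21 | 56 |
| 21 | 22 | 14 | 49 |
| 28 | 29 | 7 | 42 |
| 35 | 36 | 0 | 35 |

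Over this range, one Closing Visit row could hold samples from 1 to 10 weeks after surgery. A stay of 35 days or more produces no early sample.

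**4. Version check.** The SAP postdates protocol version 4.3 by about 21 months (September 2021 to June 2023) but cites 4.0 and 4.2 UK. Its flowchart lacks the discharge footnote and two marks present in version 4.3: urinalysis on Day 5 and coagulation factors at end of surgery. Section 12.6.3 ties descriptive statistics to visits "at each scheduled assessment visit (as stated in Flowchart of study" but exempts urinalysis. Section 8.10 already lists both Day 5 and End of Surgery. The urinalysis gap therefore changes no table. The coagulation-factor gap leaves only one descriptive row in doubt, because the shift tables cover all laboratory variables except direct and indirect bilirubin.

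**The case against.** **Testing at discharge was a deliberate, documented amendment, and no SAP wording can recover a Day 36 sample that was not taken.** True. The point concerns how such results are labelled, not whether the option should exist.

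**There are safeguards.** Adverse events are collected to the closing visit even by phone, and suspected transmission of infective agents is an adverse event of special interest, so viral safety does not rest on one shift table. Laboratory and vital signs summaries are repeated by surgery type, which separates UK from spinal data. Relative day is defined (SAP 8.20), and laboratory and viral data are listed. The TFL specifications are separate documents that are not supplied, so a date column or footnote there cannot be excluded. All of this stands and keeps the grade low. It lets a reader trace the timing, but no summary or shift table described in the SAP uses it, and the split by surgery type does not separate discharge samples from late ones within the abdominal group.

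**Stronger readings that the documents do not support.**
- *That the samples come from the first or second week.* The shortest stay category is a generic reporting bin for both surgery types, and the list runs beyond 36 days.
- *That the problem is confined to one site or to PMP subjects.* The option is shown only in the UK protocol, but the spinal protocol is not supplied.
- *That the option was used.* Nothing here shows how often, if ever.
- *That serology has a required minimum interval.* Protocol 9.2.1.4 says only screening and closing visits; the five-week figure belongs to the closing visit as a whole.
- *That the outdated flowchart loses analyses.* As shown under the version check, at most one descriptive row is in doubt.

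**Conclusion.** The concern holds as a minor one. Under the protocol's data-entry instruction and SAP 8.10, any discharge-day result from a completer will be summarised as the closing-visit result. The affected outputs are the serology shift table, the closing laboratory and coagulation-marker summaries and shifts, and the vital signs summaries. The number of subjects and the size of the timing gap are unknown. The table of gaps is an assumed range, not an estimate.

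The conclusion rests on the phone-call option being used at least once before Day 36, and on the unseen TFL specifications containing no date-based rule. The primary endpoint, the efficacy analyses and adverse event follow-up are untouched. Nothing in the protocol links the option to treatment arm, so the documents give no ground to infer a bias between BT524 and its comparator within a surgery type.

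One related passage needs reconciling within the protocol. Section 9.2.1.5 still reads "At closing visit (Day 36) an additional serum sample (5 mL) must be taken", whereas section 7.1 allows that sample on the day of discharge.

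**What to change.** Before database lock:
1. In SAP 4.0, add protocol version 4.3 UK to the base documents.
2. In SAP 8.10, map closing-visit results by actual sample date, separating discharge samples taken before Day 36 from samples taken on Day 36 or later.
3. In the serology shift table and the closing laboratory and coagulation-marker shifts, show the two groups separately and state how many subjects have no sample from Day 36 or later. Apply the same mapping to the vital signs summaries.
4. As housekeeping, refresh the SAP flowchart so that end-of-surgery coagulation factors are clearly included in the descriptive statistics.

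The cost is SAP wording and a derivation from dates that SAP 8.20 already uses for relative day. The tables for Day 36 or later will contain fewer subjects, which is a fair statement of the evidence available at that time. No study procedure changes.

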#### 7.2 Duration of the Clinical Study

First Subject in (planned)	Q1 2018
Last Subject Last Visit (planned)	tbd

#### Individual Subject

Regular duration of individual study participation for eligible screened subjects is at least 5 weeks plus time between screening (signed ICF) and surgery.

Each subject fulfilling the intra-operative inclusion criteria will be administered BT524 or cryoprecipitate during surgery. The usual stay in hospital after elective surgery varies depending on the type of surgery and subjects overall conditions. Each subject will have follow-up visits 1, 2, 4 and 7 days after surgery (Day 2, 3, 5 and 8) and the day of discharge from hospital will be recorded.

Subsequent, each subject has to attend a closing visit including the final safety examination, and a safety follow-up at least 5 weeks after surgery, scheduled on Day 36. Using a phone call for the closing visit Day 36 is acceptable if all tests and procedures scheduled for Day 36 requiring an in-person visit, were performed on the day of hospital discharge.

The closing visit can be postponed up to Day 71 (Day 36 +35) if required due to subject's availability (e.g., stay in rehabilitation center).

Subjects not meeting inclusion criteria or meeting exclusion criteria are screen failures and will end study participation at the day of screen failure. Subjects that do not meet the intra-operatively inclusion criterion are also considered as screen failure and will end study participation on the day of the surgery.

A subject is considered to have completed the study when he/she is presumed to have followed the protocol (i.e., completed visits approximately 5 weeks after surgery). If for any reason, a subject discontinues involvement in the study early, every effort should be made to ensure the subject attends a closing visit (section 4.4).

For each subject date and reason for the end of the study participation will be recorded.

# 7.2.1 End of Study

The end of clinical study will be defined as the Last Visit of the Last Subject.

# 7.3 Criteria for Premature Termination

#### 7.3.1 Premature Termination of the Entire Clinical Study

The clinical study as a whole may be stopped by Biotest after consultation with the Coordinating Investigator if there are reasons for which continuation of clinical study is no longer justified, such as:

- a) Unacceptable delay of study completion
- b) Low recruitment rate
- c) A large number of subjects with premature termination
- d) Changed benefit-risk ratio according to the efficacy and/or safety results from this or parallel studies
- e) Lack of efficacy

PPD

f) Recently emerged information suggest that the study population can be offered a more advantageous study design

In case of premature termination of the entire clinical study, the sponsor has to notify the appropriate Ethics Committees and Regulatory Authorities as soon as possible but at the latest within 15 days.

7.3.2 Premature Termination of an Individual Study Site

The clinical study may be stopped at an individual study site for reasons such as:

a) Determination of unexpected, significant, or unacceptable risk to subjects.

- b) Low recruitment rate,
- c) Lack of co-operation,
- d) Severe deviations from study protocol,
- e) Manipulation of study data,
- f) Violation of other ethical or legal principles.

# 7.4 Treatment and Care after the End of the Study

For subjects who have finished the clinical study and for all subjects who drop out prematurely it is the responsibility of the investigator to choose adequate therapeutic measurements.

After termination of the clinical study, any unexpected safety issue that changes the benefit-risk evaluation and is likely to have an impact on the subjects who have participated in it, should be reported as soon as possible to the sponsor. Sponsor expeditiously reports the event to the competent authority(ies) concerned (see also section 9.3.4).

